### 4.2.1. Primary Objective

The primary objective is to confirm that the Medtronic Hugo™ RAS System performs as intended when used for prostatectomy or cholecystectomy. Primary endpoint is below:

- Completion rate: A proportion of subjects who completed the surgery without conversion (to open or conventional laparoscopic surgery) due to system serious malfunction, and without any major complications within 24-hour post-surgery
  - \* Major complication is defined as Clavien-Dindo grade  $\geq 3$

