With regards to the previous studies, the completion rate of surgery—the primary endpoint of this study—is expected to be over 90%. The study will be considered successful when the point estimate of the completion rate is greater than or equal to 95%, which is when  $\leq 2$  patients (among 40) does not reach the surgery completion. The primary endpoint is evaluated within short period (i.e., 24-hour post surgery) period so the dropout rate is not considered. Note that it is not possible to assess the surgery completion per the study definition when a subject who inevitably converted not due to the Hugo™ RAS system. In such cases, new enrollment is allowed until the minimum sample size (i.e., 40) is reached.

In summary, the estimated sample size is adequate to demonstrate the safety and performance of the investigational device regarding following reasons: (1) the estimated sample size is higher than the number of patients from recent pivotal trial (which used the same primary endpoint) of the locally commercialized product (i.e., 32; 17 prostatectomy cases and 15 cholecystectomy cases) [11, 12], and (2) the investigational device is intended to be used for the same patient population of the commercialized product.

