***Medtronic Business Restricted***

## 9. Statistical Design and Methods

### 9.1. General Aspects of Analysis

The study analysis will occur after all patients complete the 30-day follow-up and data entry error or non-reasonable values are cleaned. Data analysis will be performed by Medtronic or its designee using SAS for Windows (version 9.4 or higher, SAS Institute Inc. Cary, NC) or other widely accepted statistical or graphical software.

Statistical tests will be conducted at a two-sided alpha level of 0.05. Confidence intervals will be presented as 95% confidence intervals.

The following populations will be considered for the analysis of data for this study:

- Full Analysis Set (FAS): The full analysis set is defined as all enrolled subjects in whom the Hugo™ RAS procedure is begun (defined as the first skin incision). In the event that a subject is consented but the first incision does not occur (e.g., if the subject becomes ineligible during the timeframe between consent and the procedure day), that subject will be excluded. Also, a subject who inevitably converted (to open or conventional laparoscopic surgery) not due to the Hugo™ RAS system will be included in the safety and other descriptive analyses but excluded from the primary endpoint analysis (since the subject is not evaluable).
- Per Protocol Set (PPS): The per protocol set is a subset of the FAS including only those without any major protocol deviations. Following subjects from the FAS will be excluded from the PPS:
  - Subject who inevitably converted (to open or conventional laparoscopic surgery) not due to the Hugo™ RAS system
  - Subject did not meet Inclusion/exclusion criteria
  - Subject chooses to withdraw
  - Failure to collect required study data up to 30-day post-surgery

The FAS will be the primary analysis set for the evaluation of the primary and secondary endpoints. Statistical analysis will be performed for each analysis set. However, if all subjects complete the study per the CIP, the results can be presented regardless of the analysis set.

Subject disposition will be illustrated in a CONSORT diagram. All enrolled subjects will be included in a subject disposition table indicating reasons for exclusion from the FAS and PPS analysis sets.

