**CONFIDENTIAL**

056-F275 Rev E Clinical Investigation Plan Template

The study will be considered successful when the primary endpoint is met: if the point estimate of the completion rate is greater than or equal to the pre-determined value (i.e., 0.95) in the FAS.

Missing data will not be imputed for the primary analysis, and multiple testing adjustments are not considered. Sensitivity analysis (e.g., multiple imputations for missing data) may be performed to ensure the study results are robust.

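### One per-protocol set for all endpoints drops subjects with known 24-hour outcomes from the supportive completion rate because of later events

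*Protocol*

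**What the plan says.** The primary endpoint is completion of surgery without a device-caused conversion and "without any major complications within 24-hour post-surgery" (Protocol 4.2.1, repeated in SAP 7.9). Protocol 6.5 uses the short window to set attrition aside when fixing the sample size: "The primary endpoint is evaluated within short period (i.e., 24-hour post surgery) period so the dropout rate is not considered".

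Protocol 9.1 and SAP 7.1.3 give the same single definition of the PPS: "The per protocol set is a subset of the FAS including only those without any major protocol deviations". The listed exclusions include "Subject chooses to withdraw", with no limit on when the withdrawal happens, and "Failure to collect required study data up to 30-day post-surgery". Neither is restricted to particular endpoints. Protocol 8.13 also names missing 30-day data as an example of a major deviation.

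Both documents then say: "Statistical analysis will be performed for each analysis set". A PPS completion rate will therefore be reported. The FAS has priority: "The FAS will be the primary analysis set for the evaluation of the primary and secondary endpoints". Protocol 9.1 ties success to a completion rate "greater than or equal to the pre-determined value (i.e., 0.95) in the FAS".

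**The concern.** A per-protocol analysis of the primary endpoint should show whether adherence to the plan, up to the point where the outcome is determined, changes the answer. Here membership also depends on what happens between 24 hours and Day 30. A subject who completed surgery and misses the Day 30 visit leaves the PPS as a known success. A subject with a grade 3 or higher complication at 12 hours who later withdraws leaves it as a known failure. Neither departure says anything about adherence at surgery.

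This fits poorly with Protocol 6.5, which treats later dropout as irrelevant to the same endpoint. The required 30-day data are also not itemised, so it is unclear whether, for example, a missing Day 14 or Day 30 laboratory test is enough to exclude. SAP 7.1.2 leaves major deviations to be identified by the study team before analysis, in an unblinded single-arm trial.

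What is at stake is how the supportive result is read. A PPS rate on the other side of 0.95 from the FAS rate would invite an explanation in terms of protocol adherence that need not be true.

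**Working it through.** **Inputs from the documents.** N = 40, with 20 per procedure; threshold 0.95 on the point estimate, judged in the FAS; 24-hour outcome window; PPS exclusions as above. Intervals are exact (Clopper-Pearson) 95%.

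**Inputs not in the documents, assumed.** Probability q that a subject is lost to the PPS after 24 hours: 2.5% to 5%, independent of outcome. True completion rate: 95%, with 98% as a second case.

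**1. The plan's own figure.** Protocol 6.5 allows at most 2 non-completers in 40. With f failures the rule is (40 − f)/40 ≥ 0.95, so f ≤ 2: 38/40 = 95.0% passes and 37/40 = 92.5% does not. The figure is reproduced.

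**2. Effect of later exclusions.** If d failures and s completers are dropped, the PPS rate is (40 − f − s)/(40 − d − s).

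| FAS | Dropped after 24 hours | PPS | 95% CI |
|---|---|---|---|
| 38/40 = 95.0% | 1 completer | 37/39 = 94.9% | 82.7 to 99.4 |
| 38/40 = 95.0% | 1 failure | 38/39 = 97.4% | 86.5 to 99.9 |
| 37/40 = 92.5% | 1 failure | 37/39 = 94.9% | 82.7 to 99.4 |
| 37/40 = 92.5% | 2 failures | 37/38 = 97.4% | 86.2 to 99.9 |

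The margin is thin because 5% of 40 is exactly 2, while 5% of any size from 30 to 39 lies between 1.5 and 1.95. A PPS of that size tolerates only one failure. In the by-procedure presentation of SAP 7.9, 19/20 = 95.0% becomes 18/19 = 94.7% if one completer is dropped.

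**3. How often the FAS meets 0.95 and the PPS does not.** In practice this needs exactly two failures, both retained, and at least one of the 38 completers dropped:

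P = C(40,2) × 0.05² × 0.95³⁸ × (1 − q)² × [1 − (1 − q)³⁸]

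- q = 2.5%: 0.2777 × 0.9506 × 0.6179 = 0.163
- q = 5%: 0.2777 × 0.9025 × 0.8576 = 0.2149

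That is about 16% to 21%. With 98% true completion the first factor is 0.1448, and the results are about 9% and 11%.

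**4. The reverse, FAS below 0.95 and PPS at or above it.** Summing over all combinations under the same assumptions gives 0.03% to 0.14% at 95% true completion, and under 0.03% at 98%.

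**5. After the change.** If every subject with a known 24-hour outcome stays in the primary-endpoint PPS, later dropout cannot move it. Two failures remain 38/40 = 95.0% (83.1 to 99.4), and three remain 37/40 = 92.5% (79.6 to 98.4).

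**The case against.** The strongest reply is that nothing decisive depends on the PPS. Success is defined in the FAS, which has no withdrawal or 30-day exclusion, so a known 24-hour failure stays in the deciding analysis. This stands in full. A PPS of 37/39 fails no criterion, and 0.95 serves above only as a reference line.

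It can also be said that the PPS is a deliberate completer set. The synopsis describes it as subjects who completed the study according to the plan, and the 30-day exclusion follows the deviation list in Protocol 8.13. That is fair: the rule is internally derived, and the sample-size remark in 6.5 does not formally contradict it. It remains a poor set for a 24-hour endpoint.

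Safeguards exist. A disposition table must give reasons for exclusion from each set, Protocol 8.8 allows use of data collected up to exit, and Protocol 12.17 asks for every effort to complete each subject's follow-up. These make a discrepancy traceable but do not restore the excluded subjects.

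A reader might infer that anyone who dies before Day 30 is removed. The text does not compel this. Protocol 8.8 lists death separately from voluntary withdrawal, and only the latter is a PPS exclusion. The synopsis ends participation at death, so later data are arguably no longer required, and Protocol 8.13 defines a deviation as something not done according to the plan. The treatment of death is unstated.

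**Conclusion.** The point holds as a minor defect in a supportive analysis. Applied as written, the PPS completion rate discards known 24-hour outcomes because of later withdrawal or missing 30-day data, and can disagree with the FAS for reasons unrelated to adherence at surgery. Under the assumed 2.5% to 5% loss, independent of outcome, the FAS meets 0.95 and the PPS falls below it in about 16% to 21% of trials at 95% true completion, and in about 9% to 11% at 98%. These figures depend on rates that the documents do not give.

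Two stronger readings should be avoided. One is that the success decision is at risk; it is not, because it rests on the FAS. The other is that the rule mainly flatters the device. The 37/40 to 37/38 case needs two of three failures to exit early, and the flattering reversal is negligible (at most 0.14%) unless loss is tied to failure. Protocol 8.8 makes such a link possible by listing unacceptable adverse events as an exit reason, but the documents do not quantify it. With loss independent of outcome, the likelier shift across 0.95 makes the PPS look worse than the FAS. Nor is the chance that at least one subject is dropped (1 − 0.975⁴⁰ = 64% to 1 − 0.95⁴⁰ = 87%) a measure of harm, since most such losses leave the comparison with 0.95 unchanged.

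**What to change.** In Protocol 9.1 and SAP 7.1.3, make the PPS endpoint-specific:

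- **Primary endpoint:** FAS subjects evaluable for that endpoint who met the eligibility criteria, had no major deviation up to the end of the 24-hour window, and have a known 24-hour outcome, regardless of later withdrawal or missing Day 30 data.
- **30-day secondary endpoints:** apply the withdrawal and 30-day completeness exclusions here only, and list which data items count as required.
- **Death and exit after an event:** state that death, or exit after a recorded complication, readmission or reoperation, does not by itself count as failure to collect data. The eligibility and surgery-deviation exclusions still apply to such subjects.

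The cost is an amendment to wording in both documents. No further data are needed, and neither the sample size nor the FAS success rule changes.

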**CONFIDENTIAL**

056-F275 Rev E Clinical Investigation Plan Template

The study will be considered successful when the primary endpoint is met: if the point estimate of the completion rate is greater than or equal to the pre-determined value (i.e., 0.95) in the FAS.

Missing data will not be imputed for the primary analysis, and multiple testing adjustments are not considered. Sensitivity analysis (e.g., multiple imputations for missing data) may be performed to ensure the study results are robust.

## 9.2. Pre-operative Characteristics

Descriptive statistics will be used to summarize pre-operative characteristics of subjects per indication, including: demographics, medical history, vital signs, laboratory test results, ASA class, etc.

## 9.3. Surgical Data

Descriptive statistics will be used to summarize procedure information, including but not limited to: setup time, console time, total operative time, takedown time, estimated blood loss, conversion to open/laparoscopic surgery, blood transfusion during the surgery, length of hospital stay, delay in robot setup time, and delay in total operative time.

## 9.4. Primary Endpoint

The Clopper-Pearson Exact test for single proportion will be conducted. The number of subjects successfully completed the surgical procedure, percentage, and its 95% confidence interval will be summarized. If the point estimate of the completion rate is greater than or equal to the pre-determined value (i.e., 0.95), it is considered that the primary objective is met.

## 9.5. Secondary Endpoints

Descriptive statistics will be used. Frequency, percentage, and its 95% confidence interval will be presented for each secondary endpoint: overall complication rate through 30-day post-surgery, major complication rate through 30-day post-surgery, readmission rate through 30-day post-surgery, reoperation through 30-day post-surgery, and DD rate. The Clopper-Pearson Exact test with 95% confidence interval for single proportion will be conducted.

Any post-operative complication or major complication will be summarized by MedDRA term (system organ class and preferred term), along with the number of events and the number of subjects with an event. Regarding DD, the number of DDs and the number of subjects with a DD shall be presented.

## 9.6. Other Pre-Specified Measures

Descriptive analyses of other pre-specified measures beyond the primary and secondary objectives will be performed for followings: AE rate, pathological findings (only for prostatectomy subjects).

AEs during the study period will be summarized by MedDRA term (system organ class and preferred term), along with the number of events and the number of subjects with an event.

## 9.7. Interim Analysis

No interim analyses are planned for this study.

## 9.8. Subgroup Analyses

Subgroup analyses may be used to explore the safety and performance of the study device given various patient, medical, and procedural factors. Subgroup factors include below but not limited to:

- Sex (Male vs. Female) (Cholecystectomy only)
- Age group
- ASA class
- Obesity (BMI <25 kg/m^2 vs. BMI ≥25 and <30 kg/m^2 vs. BMI ≥30 kg/m^2)
- Comorbidities (Yes vs. No)
- Procedure-specific characteristics (e.g., nerve-sparing in prostatectomy)

## 10. Adverse Events and Device Deficiencies

### 10.1. Adverse Events and Device Deficiencies

All AEs will be collected throughout a subject's participation, starting from the time the IC is provided, regardless of their severity or relationship to the Hugo™ RAS or study procedures. Assessment of the occurrence of an AE will be based on changes in the subject's physical examination, laboratory results, and/or signs and symptoms. Reporting of these events to the sponsor will occur on an AE CRF, including date of AE, event description, treatment, resolution, assessment of both the seriousness of the AE and the relatedness to the system components. The completed AE CRF must be submitted to Medtronic as soon as possible.

In addition, DD information will be collected throughout the study and reported to the sponsor on a DD CRF. Note that DDs that result in an AE to the subject should be captured as an AE only. DD that could have led to a serious adverse device effect (SADE) (i.e., if suitable action had not been taken, if intervention had not been made, or if the circumstances had been less fortunate) require immediate reporting.

Upon receipt of AE or DD at Medtronic, a sponsor representative will review the AE/DD for completeness and accuracy and when necessary will request clarification and/or additional information from the investigator. If the event is unanticipated or unanticipated serious ADE, the sponsor will review the specific details behind those observations and determine what, if any, action is appropriate.

For any changes in status of a previously reported AE or DD (i.e., change in actions taken, change in outcome, change in relatedness), information needs to be updated on, or added to the original AE or DD CRF.

All AEs must be followed until the AE has been resolved, is unresolved with no further actions planned, the subject dies or exits the study, whichever occurs first. At the time of study exit, all collected AEs that are unresolved must be reviewed and an update to the original AE must be reported.

Adverse events that have not resolved at the time of the subject's discontinuation or completion of the study should have an outcome of Not Recovered/Not Resolved at study end in subject source and on eCRF. The investigator should ensure that subject is aware of any follow-up or additional treatment that is required for any ongoing AE at the end of study participation; however, there will be no eCRF entry for the ongoing follow-up.

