### 4.2.2. Secondary Objective

The secondary objective is to assess the short-term safety outcome of the Medtronic Hugo™ RAS System when used for prostatectomy or cholecystectomy. Secondary endpoints are below:

- Overall complication rate through 30-day post-surgery: A proportion of subjects with any post-operative complication within 30-days post-surgery using the investigational device
- Major complication rate through 30-day post-surgery: A proportion of subjects with any post-operative complication classified  $\geq 3$  by the Clavien-Dindo system within 30-days post-surgery using the investigational device

*Medtronic Business Restricted*

- Readmission rate through 30-day post-surgery: A proportion of subjects hospitalized within 30 days post-surgery
- Reoperation rate through 30-day post-surgery: A proportion of subjects go through reoperation for the same indication within 30 days post-surgery
- Device deficiency rate: A proportion of subjects with any device deficiency (DD) during robotic assisted surgery using the investigational device

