## 8.5. Surgical Procedure (Day 0)

The subject will arrive for admission to the hospital and prepped for surgery. On the day of surgery, the subject will receive a robotic assisted prostatectomy or cholecystectomy per indication. Pre-operative and operative procedures are according to local standard practices. The following information is required to be collected at the surgery visit:

- Pre-operative vital signs: pulse rate (bpm), respiration rate (bpm), blood pressure (mmHg), body temperature (°C)
- Procedure information
  - Date of admission, date of surgery

- Operative time: Setup time, console time, total operative time (skin to skin time), takedown time
- Estimated blood loss (mL)
- Conversion: Conversion to open/laparoscopic surgery during procedure (and reason for conversion, if conversion occurs)
- Blood transfusion: Blood transfusion during surgery (and the number of blood pack used if transfusion required)
- Changes to port placement (and reason for change, if occurs)
- Delay in robot setup time or total operative time (and reason for delay, if occurs)
- Device information: Lot number, software version, compatible instruments
- Other measurements: Collected per indication
  - Prostatectomy: Pelvic lymph node dissection, nerve-sparing prostatectomy
  - Cholecystectomy: Amount of gallbladder adhesions, concomitant gallbladder stones, type of gallbladder polyps (if applicable), acute cholecystitis, other concomitant procedures, use of drainage tube
- Medication: Brand name, indication (see Section 8.9 for details)
- Adverse event (if any): Diagnosis, seriousness, severity, Clavien-Dindo grade, action taken, outcome, relatedness, etc.
- Device deficiency (if any): Diagnosis, applicable device information (e.g., device type, Lot number, etc.)

In addition to above, below information is to be collected immediately after prostatectomy.

- Laboratory tests: Complete blood cell, serum chemistry (e.g., Complete blood cell (RBC, WBC, Hb, Hct, Platelet, ESR, etc.), admission panel (Glucose, Calcium, Phosphorous, BUN, Uric acid, Creatinine, eGFR (MDRD), AST, ALT, ALP, Total bilirubin, Albumin, Total protein, etc.), electrolyte panel (Sodium, Potassium, Chloride, etc.),
- Post-operative imaging (only collected if it is related to adverse events): Chest X-ray (Chest AP) findings, abdomen supine X-ray findings

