**Table 7. Adverse Event and Device Deficiency Definitions**

General	
Adverse Event (AE)*	
Any untoward medical occurrence, unintended disease or injury, or untoward clinical signs (including abnormal laboratory findings) in subjects, users or other persons, whether or not related to the investigational medical device and whether anticipated or unanticipated.
 
NOTE 1: This definition includes events related to the investigational medical device or the comparator. NOTE 2: This definition includes events related to the procedures involved. NOTE 3: For users or other persons, this definition is restricted to events related to investigational medical devices or comparators. (ISO 14155:2020 section 3.2) *The ISO 14155 definition is equivalent to AE under KGCP Article 2 item M.

Adverse Device Effect (ADE)*	
Adverse event related to the use of an investigational medical device
 
NOTE 1: This definition includes adverse events resulting from insufficient or inadequate instructions for use, deployment, implantation, installation, or operation, or any malfunction of the investigational medical device. NOTE 2: This definition includes any event resulting from use error or from intentional misuse of the investigational medical device. NOTE 3: This includes 'comparator' if the comparator is a medical device. (ISO 14155:2020 section 3.1) * The ISO 14155 definition is equivalent to ADE under KGCP Article 2 item N.

Unanticipated Adverse Device Effect (UADE)	
Deviation from the aspect of ADEs or the degree of harm reflecting from the available medical device related information such as investigator's brochure or medical device package insert (KGCP Article 2 item P)

Device Deficiency (DD)	
Inadequacy of a medical device with respect to its identity, quality, durability, reliability, usability, safety or performance
 
NOTE 1: Device deficiencies include malfunctions, use errors and inadequacy in the information supplied by the manufacturer including labeling. NOTE 2: This definition includes device deficiencies related to the investigational medical device or the comparator. (ISO 14155:2020 section 3.19)

Relatedness	
Study Device	
An AE that results from the presence or performance of any component of the system and its compatible components

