### 12.2. CIP Amendments

Any revisions or amendments to the CIP or IC document, will be submitted to the MFDS and/or IRBs along with a statement of justification for changes, for their approval prior to implementing the amendment. All amendments to the CIP shall be agreed upon between Medtronic and the principal investigator(s), or the coordinating investigator. Subject enrollment must stop until the amendment is approved.

Minor amendment including administrative changes to the CIP will be submitted to the MFDS and/or IRB for notification, if applicable. Minor amendments do not necessarily require MFDS approval.

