7.10 Safety Evaluation

Safety will be assessed as the proportion of subjects with Adverse Events (AE) based on the FAS and count of AEs. incidence will be reported overall, and according to:

- Severity
- Seriousness
- Relation to the device
- Relation to the procedure
- Adverse Device Effects (Serious and Non-Serious Procedure and/or Device Related AEs)
- Serious Adverse Device Effects (Serious Procedure and/or Device Related AEs)

Listings of AEs by MedDRA terms and Death will be presented.

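### Device deficiencies that cause an adverse event are recorded only as adverse events, so the device deficiency rate leaves them out

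*Protocol*

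**What the plan says.** **Capture.** Protocol Section 10.1 first sets a general rule: "DD information will be collected throughout the study and reported to the sponsor on a DD CRF". The next sentence makes an exception: "Note that DDs that result in an AE to the subject should be captured as an AE only".

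**Endpoint.** Protocol 4.2.2 and SAP 7.9 define the DD rate in the same words: "A proportion of subjects with any device deficiency (DD) during robotic assisted surgery using the investigational device". Protocol 8.11 lists it among the endpoints that assess the safety of the device.

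**Definition.** Table 7 describes a DD as a shortcoming of the device itself and adds: "Device deficiencies include malfunctions, use errors and inadequacy in the information supplied by the manufacturer including labeling". It does not exclude deficiencies that lead to harm.

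**Surgery visit.** Protocol 8.5 lists among the required items: "Device deficiency (if any): Diagnosis, applicable device information (e.g., device type, Lot number, etc". It mentions no exception for deficiencies linked to an AE.

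**Analysis.** Protocol 9.5 and SAP 7.9 contain the same sentence: "Regarding DD, the number of DDs and the number of subjects with a DD shall be presented". Neither says that AE records are to be searched for deficiencies.

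**The concern.** The endpoint asks how many subjects had any deficiency, but the capture rule keeps one kind of deficiency off the DD form: the kind that resulted in an AE. A malfunction that injured a patient would be a DD under Table 7 and would still have no DD record.

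The DD rate is the one secondary endpoint that measures device performance directly. If the rule is followed and DDs are counted from the DD form, the error has one direction, downward, and it selects on harm. The deficiencies that remain are those without clinical consequence. The plan also leaves room for two analysts to report different rates from the same data, one counting DD forms alone and the other searching the AEs as well.

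**Working it through.** **1. Is there a route back into the count?** The plan states no expected or target DD rate, so there is no figure to reproduce; the check is of the text.

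| Step | Place | Treatment of a DD that causes an AE |
|---|---|---|
| Definition | Protocol Table 7 | It is a DD |
| Endpoint | Protocol 4.2.2, SAP 7.9 | Counted, since any DD qualifies |
| Visit data | Protocol 8.5 | Collected, no exception stated |
| Capture rule | Protocol 10.1 | AE record only |
| Analysis | Protocol 9.5, SAP 7.9 | Silent on AE records |
| AE summaries | SAP 7.10 | Reported as an AE, not as a DD |

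The event stays in the safety data. SAP 7.10 breaks AEs down by "Relation to the device", among other factors. That does not identify a deficiency: Table 7 treats an AE as device-related if it results from the presence or performance of a component, which can happen with no malfunction, use error or labeling fault. The adverse device effect line in SAP 7.10 also pools procedure-related with device-related AEs.

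Two consequences follow. The number of DDs loses every deficiency that led to an AE. The number of subjects with a DD loses only subjects all of whose deficiencies led to an AE; a subject with a separate harmless deficiency is still counted.

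**2. Size per subject lost.** Inputs: 40 subjects, 20 per procedure (Protocol 7.2); exact Clopper-Pearson 95% intervals (Protocol 9.5); results overall and by procedure (SAP 7.9). One subject is 1/40 = 2.5 points overall and 1/20 = 5 points within a procedure.

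For x of n, the lower limit is the 0.025 quantile of Beta(x, n − x + 1) and the upper limit is the 0.975 quantile of Beta(x + 1, n − x). The lower limit is 0 when x = 0.

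| Count | Rate | 95% CI |
|---|---|---|
| 3/40 | 7.5% | 1.6% to 20.4% |
| 2/40 | 5.0% | 0.6% to 16.9% |
| 1/40 | 2.5% | 0.1% to 13.2% |
| 0/40 | 0% | 0% to 8.8% |
| 1/20 | 5.0% | 0.1% to 24.9% |
| 0/20 | 0% | 0% to 16.8% |

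A true 3/40 is reported as the second, third or fourth row if one, two or three of those subjects had only deficiencies that caused an AE. Within a procedure, 1/20 becomes 0/20.

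**3. How likely is a loss?** The documents do not give the share *s* of deficiencies that cause an AE. I assume 10% to 50%. For the rate *m* of subjects with a deficiency I use the da Vinci malfunction figures in Protocol 6.5 (average 3%, range 0.4% to 8.0%; below 2% in Korea) as a rough stand-in, since the DD definition is broader than malfunction. With one DD per affected subject and independent subjects:

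- expected subjects lost = 40 × m × s
- chance of losing at least one = 1 − (1 − m × s)^40

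| m | Expected loss (s = 10% to 50%) | Chance of at least one |
|---|---|---|
| 0.4% | 0.016 to 0.08 | 2% to 8% |
| 2% | 0.08 to 0.4 | 8% to 33% |
| 3% | 0.12 to 0.6 | 11% to 45% |
| 8% | 0.32 to 1.6 | 27% to 80% |

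For example, at 3% and a share of 50%, 1 − (1 − 0.015)^40 = 0.454. At 8% and 50%, 1 − 0.96^40 = 0.805 (0.8046 before rounding).

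**The case against.** The strongest reply is that Section 10.1 governs which form is completed, not what is analysed. Protocol 9.5 and SAP 7.9 ask for the number of DDs without naming the DD form as the source. Table 7 still makes a harmful deficiency a DD, so an analyst could count it from the AE record and remain within the endpoint. On this reading the plan lacks a derivation rule but does not order an omission. It is true that the analysis sections name no source. But the only stated place for a DD is the DD form, the exception removes these events from it, and no rule finds them again. Carrying out what is written gives the undercount.

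Second, such events are reported and partly traceable. The adverse device effect definition in Table 7 expressly covers AEs from malfunction, use error and inadequate instructions; the AE form holds a description and relatedness to the system components; and reasons for conversion and delay are recorded at surgery. This stands as a limit on the harm, but none of it rebuilds the numerator. The sample case report form is under separate cover, so a DD flag on the AE form cannot be ruled out. Neither document mentions one, and a flag would still need a counting rule.

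Third, the visit list in 8.5 is weak evidence, because a general checklist need not repeat a specific exception. That is fair, and the finding does not depend on it.

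Fourth, the probabilities rest on an assumed share and a borrowed rate. That is also fair. They illustrate the range; the firm figures are 2.5 and 5 points per subject lost.

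Finally, the endpoint has no threshold and SAP 7.5 calls the analyses descriptive. This limits the severity but does not remove the inconsistency.

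**Conclusion.** The concern holds. The capture rule in Section 10.1 conflicts with the any-deficiency endpoint, and nothing in either document reconciles them. The bias is downward only and falls on deficiencies that caused an AE. The per-subject effect takes 40 subjects as the denominator; the full analysis set may be slightly larger, because subjects converted for reasons unrelated to the system remain in it for safety and may be replaced. The number of subjects affected is unknown and could be none.

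The primary endpoint does not depend on the DD form: Protocol 8.10 takes conversion from the surgery record, and the success rule in 9.1 uses only the completion rate. This should be fixed before analysis, but it does not threaten the trial's main conclusion.

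**What to change.** **Preferred.** Replace the exception in Protocol 10.1 with: *A DD that results in an AE is recorded on both the DD CRF and the AE CRF, and the two records are linked.* In Protocol 9.5 and SAP 7.9 add: *The DD numerator is all subjects with any DD during surgery, with or without an associated AE; the two groups are also shown separately.* State how a linked event is handled in Table 11, which has separate reporting rows for adverse device effects and for DDs.

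Cost: one protocol sentence, the matching lines in Protocol 9.5 and SAP 7.9, CRF instructions, and a second short form for a few events. The amendment goes to the MFDS and/or IRB, and under Protocol 12.2 "Subject enrollment must stop until the amendment is approved", unless it is classed as minor.

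**If a protocol amendment is impractical.** Amend only SAP 7.9: *DDs are all DD CRF entries plus all AEs that a documented review before database lock identifies as arising from a malfunction, use error or other DD as defined in Table 7. The DD rate counts those that occurred during surgery.*

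Cost: one SAP amendment and a review of device-related AEs in about 40 subjects. Site procedures do not change, though a few queries may be needed where the AE description does not show whether a deficiency occurred.
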